#### 4.2 Visit Schedule

The following schedule is for data collection only. Less frequent visits are not allowed, although more frequent visits may be allowed, as clinically indicated. Each clinic visit will be documented on the Clinic Visit Form (whether it be a data collection visit or a clinically indicated visit for a dose adjustment, or for a prescription).

VISIT DAY DAY -28	GROUP/PHASE All Participants/Induction	MAX. PRESCRIPTION 7 DAYS
DAY -25	All Participants/Stabilization (This visit may occur anytime bety Days -26 and -22)	ween 8 DAYS
DAY -21	All Participants/Stabilization (This visit may occur anytime betwood Days -21 and -15)	ween 8 DAYS
DAY -14	All Participants/Stabilization (This visit may occur anytime betwood Days -14 and -8)	ween 8 DAYS*
DAY -7	All Participants/Stabilization (This visit may occur anytime bety Days -7 and -1)	ween Enough to last through Day 0*

\*With Instructions to remain on stable dose from day -7 through day 0.

Protocol # CTN-0003

Page 15 of 44

Version 7C

VISIT DAY	GROUP/PHASE	MAX. PRESCRIPTION
DAY 0	All Participants/RANDOMIZATION (3 day window - post - but becomes Day	y 0) 7 DAYS
DAY 7* (*G1 Day 8)	Group #1 – END OF TAPER VISIT One visit on Day 8* (3 day window - po Group #2 - One visit between days 1 and	
DAY 14	Group #1 - One visit between days 9 an Group #2 - One visit between days 8 an	
DAY 21	Group #1 - One visit between days 15 a Group #2 - One visit between days 15 a	
DAY 28** (**G2 Day 29)	Group #1 - One visit between days 22 a Group #2 – END OF TAPER VISIT One visit on Day 29** (3 day window -	NONE
DAY 35	Group #1 - 1 MONTH POST TAPER F One visit between days 29 and 35 (7-da Group #2 - One visit between days 30 a	y window - post)
DAY 42	All Participants - Post Taper Visit One visit between days 36 and 42	NONE
DAY 49	All Participants - Post Taper Visit One visit between days 43 and 49	NONE
DAY 56	Group #1 - One visit between days 50 a Group #2 - 1 MONTH POST TAPER F One visit between days 50 and 56 (7 day	FOLLOW-UP NONE
DAY 84	All Participants-3 MONTH POST RAN FOLLOW-UP -One visit between days (7 day window - post)	
DAY 91	Group #1 only - 3 MONTH POST TAP One visit between days 85 and 91 (7 day window - post)	PER FOLLOW-UP  NONE
DAY 112	Group #2 only –3 MONTH POST TAP One visit between days 106-112 (7 day window - post)	ER FOLLOW-UP NONE

Protocol # CTN-0003

Page 16 of 44

Version 7C
Date of Preparation: 1/31/05

## 4.3 Induction

To facilitate a comfortable transition onto Suboxone (the BUP/NX combination tablet), participants will be instructed not to use any heroin or other opiates for at least 6 hours prior to the time scheduled to receive their first dose of Suboxone. Study staff at each site will document the time of last drug use and verify any signs and symptoms of withdrawal. On the day of induction, prior to taking the first dose, a urine drug screen will be obtained. Participants providing a screen positive for methadone or benzodiazepines will not be inducted onto Suboxone. Female participants of childbearing potential must also provide a negative pregnancy test on the day of induction. Withdrawal signs and symptoms, vital signs, adverse events, concomitant medications, and craving scores will also be obtained prior to induction. Vital signs will be assessed one hour after first study drug administration to ensure stability before the participant leaves the clinic.

Induction will be defined as the first 3 days of the study (-28, -27, -26) for the purpose of this protocol. The first dose of 2mg or 4mg (expressed as amount of buprenorphine) will be taken sublingually and dispensed in the clinic. Participants will be instructed to hold the tablet(s) under their tongue until the medication has dissolved. Participants will be asked to remain in the clinic for a minimum of one hour to monitor for adverse effects. Participants may receive an additional dose in the clinic at the study physician's discretion. The total dose for day -28 may not exceed 8mg (it may be less than 8mg but no more than 8mg) and may be given entirely in the clinic or part in the clinic and part at home (i.e., 4mg given in clinic and 4mg to take home). Participants should be prescribed and dispensed enough medication to continue dosing until the next scheduled office visit (no more than seven days prescription should be given on induction day). Participants will be asked to make contact with study staff on the following day and will attend the clinic and be seen by study medical staff, at a minimum, one additional day during the first week (between days -26 and -22). Office visits may be scheduled more frequently, at the study physician's discretion. The targeted induction doses, which cannot be exceeded, for days -28, -27 and -26 are as follows: Day -28 (8mg), Day -27 (12mg) and Day -26 (16mg). A daily dose, lower than the target dose, may be allowed if clinically indicated. At the next scheduled visit (between days -26 and -22), participants will be seen for vital signs, evaluation of drug use (self-report and urine screen), craving, signs and symptoms of opiate withdrawal or over medication, any adverse events, and concomitant medication (CM) use. At this visit, the dosage may be adjusted, in 4 or 8mg increments, to between 8mg and 24mg of buprenorphine. A dosing log (DL) will be completed.

All participants will sign and be given a copy of the Suboxone Information Sheet and the Treatment Agreement outlining proper use of medication for take home dosing. A wallet card will be provided to each participant in the research. This card will detail that the person carrying the card is participating in a clinical trial and is taking the drug Suboxone. This wallet card will list both local and national emergency contact numbers for study medical personnel. All participants will return to the CTP at least one additional day during the first week (between days -26 and -22). Individual sites may require more frequent contact with participants than is required for this protocol. Additional visits will

Protocol # CTN-0003 Version 7C

be documented by filling out the Clinic Visit (CV) CRF, but no additional data will be collected during these extra visits (i.e. COWS, ARSW, etc). If a participant's dose is changed or they are dispensed medication during one of these extra visits, this information should be recorded on the Clinic Visit Form. Participants will not be paid for extra visits over and above those scheduled on the time and event schedule.

If a subject complains of withdrawal symptoms while participating in the research study, the provision of ancillary medications, by prescription, will be at the discretion of the study physician at each site. The study physician may choose to provide a prescription to any participant for ancillary medication (other than benzodiazepines) and the participant's use of medications will be recorded on the concomitant medication form at each visit. Study physicians should also note in the clinical chart that such a prescription was provided to the participant.

## 4.4 Stabilization (with flexible dosing)

Days -25 to -1 comprise the flexible dosing period because prior clinical trials have suggested that individuals vary in their tolerance and treatment response to Suboxone doses. At each scheduled weekly visit during the flexible dosing period, the study physician may adjust the participant's dose in increments of 8mg. The maximum allowable dose is 24mg per day, and the minimum allowable dose is 8mg per day. Dose changes are to be made following participant assessment. At each visit, the study staff will obtain vital signs, evaluation of illicit drug use (self-report and urine), craving, signs and symptoms of opiate withdrawal or over medication, any adverse events, and concomitant medication taken since the last visit. A dosing log will also be completed at each visit. Any additional visits, during this period for clinical indications, will be documented on the Clinic Visit CRF.

All participants are to receive a constant, stable dose of Suboxone on days -7 through 0 of either 8, 16 or 24mg of buprenorphine per day (no dose adjustments may be made by the study physician after day -7).

#### 4.5 Randomization

Participants completing the pre randomization period (-28 to -1) will be randomly assigned, on day 0, to one of two taper schedules. If for some reason, the participant is unable to attend on day 0, there will be a 3 day window following day 0 for randomization to occur. All participants must be randomized by the third day, or they will be dropped from participation. Participants who do not complete the stabilization period, or who are not randomized, may be replaced in order to obtain the appropriate randomized sample size per site. Regardless of the actual day on which participants are randomized, the day of randomization becomes day 0. The first day of either taper schedule begins on Day 1. On Randomization Day 0, participants will be given the medication for the taper, explicit written instructions detailing exactly how to take the medication for the next seven days, and told to begin the taper with the first dose on the following day (Day 1).

Protocol # CTN-0003

Page 18 of 44

Version 7C

Although participant assignment to group will be performed at the site (CTP), the randomization cards will be prepared in advance by the Data Management Group of the Pacific Region Node (Lead Node). We expect some variation in the number of participants stabilized on each of the three doses, and we will provide sites with an adequate supply of randomization envelopes for each dose. Each CTP will receive three sets of randomization cards: one set for participants on the 24 mg dose, one set for participants on the 16 mg dose, and one set for participants on the 8 mg dose. Research assistants will be instructed simply to pull the next consecutive card from the pile corresponding to the participant's dose at the time of randomization. Participants will be assigned to the tapering schedule using a 1:1 ratio of random assignment; that is, regardless of the stabilization dose, each participant will have an equal chance of being assigned to the 7 day or the 28 day taper schedule. Participants will participate in treatment as usual at each site (CTP) during screening, stabilization, tapering and follow-up, or may be referred, following taper, to other appropriate treatment services.

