#### 1.0 Background and Rationale

For decades clinicians have been frustrated by the inability to adequately detoxify opiate addicts because opiate-based detoxification, one of the most effective means to achieving that goal, has been unavailable outside the very restrictive confines of narcotic treatment programs (NTPs). This frustration has been more acutely felt over the past several years because of the rise in heroin use and the recent interest in ultra-rapid opiate detoxification, which unfortunately, has often been more a matter of commerce than medicine. Buprenorphine (Subutex), and BUP/NX (Suboxone) in particular, may change all of that.

Buprenorphine is a high affinity, partial  $\mu$ -opioid agonist recently approved by the FDA as a pharmacotherapy for opioid dependence (Bickel and Amass, 1995; Ling et al., 1994). Treatment with buprenorphine in the United States will emphasize the use of Suboxone, a sublingual combination tablet containing buprenorphine and naloxone in a 4:1 ratio (Chiang and Hawks, 1994; Chiang et al., 1996a, 1996b, Fudala et al., 1998). This combination tablet was developed to help mitigate potential diversion and abuse of buprenorphine. Bioavailability studies with sublingual solution and tablet formulations of buprenorphine indicate that in short term administration the tablets approximate 60-70% of the corresponding sublingual solution dose (Nath et al., 1999; Schuh and Johanson, 1999; Ling et al., unpublished). Thus, combination tablet dosages used in clinical practice may need to exceed those shown to be effective in prior controlled studies with the sublingual solution, although with chronic administration, the blood levels of the tablet and liquid formulations appear to approach each other (Ling et al., unpublished). While much of the treatment outcome data on opiate pharmacotherapy suggests that for most participants with chronic addiction, long-term treatment is required, many participants nevertheless desire tapering from opiate maintenance, and there are suggestions that some of these participants, i.e. those who achieve significant clinical improvement, may do well. Difficulties in tapering from methadone, the most widely used agonist for maintenance treatment, have posed a significant challenge to such therapeutic attempts. The unique pharmacological profile of buprenorphine may allow for more successful tapering after stabilization.

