## 3.0 Study Design

This is a randomized, parallel-group, open-label study. After screening and baseline assessments, participants will receive a three-day Suboxone induction and a 25 day stabilization, (total 28 day stabilization phase). For three weeks (days -28 to -8) the dosing is flexible, but in the final week of the stabilization phase (days -7 to -1 and randomization day 0), participants must be on a stable dose of either 8mg, 16mg, or 24mg of buprenorphine. On day 0 participants will be randomly assigned in a 1:1 ratio to one of two Suboxone tapering regimens. If, for some reason, the participant is unable to attend on day 0, there will be a 3 day window for randomization to occur. Regardless of the actual day on which randomization occurs, it will be named as day 0 (it may occur up to, but no longer than, three days after the actual day 0). Randomization will be stratified, within site, according to the dose being taken on day 0 (8, 16 or 24 mg of buprenorphine). Tapering regimen #1 will be performed over 7 days and regimen #2 will be performed over 28 days. Participants in both groups will be seen weekly for data collection through day 56, followed by a 3 month post randomization visit on Day 84 for both groups and a 3 month post taper follow-up on days 91 and 112 respectively. This design will allow the investigators to analyze the data in either a post taper or a post randomization design. All participants will participate in an equal number of data collection visits throughout the study. Data will be available for 1 and 3 Months Post Taper, as well as 1 and 3 Months Post Randomization.

The maximum length of study participation is expected to be approximately 5 months, including screening, stabilization, tapering, post-tapering and follow-up. All participants will also participate in TAU from the time of consent through at least the end of the taper, at the CTP that manages their study participation. Following the taper, participants may continue in TAU at the CTP or be referred to other available local resources.

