#### **4.7 Administrative Withdrawal**

Participants in the pre randomization, stabilization phase of the study will be administratively withdrawn if they miss one full week (7 consecutive days) of medication at any time. The reason for this administrative withdrawal is that such participants would not have adequate opportunity to stabilize on the appropriate dosage of buprenorphine. Participants who are administratively withdrawn for this reason will be replaced by new participants to provide the required sample of randomized participants.

Participants in the 28 day taper schedule who miss one full week (7 consecutive days of medication) at any time during the taper will be considered to have completed their taper and will not be restarted on study medication. However, such participants may continue to attend all scheduled study visits and will be considered active participants for the purposes of all other study activities and for data analysis. If these participants choose not to continue to attend study visits they will be withdrawn/terminated. The reasons for not resuming the taper on such participants are as follows: 1) participants who have relapsed to illicit opioid use would require re-induction onto buprenorphine. The re-induction would require several days, and it would be difficult then to reestablish them on their protocol dictated taper schedule; 2) participants who have not relapsed to illicit opioid use would be better served clinically to remain off opioid agonist therapy since the ultimate goal is to reduce the buprenorphine dosage to zero, which they have effectively accomplished.

At any time during the study, if any participant misses three consecutive scheduled visits prior to Day 84 (a period of one month), he/she will be terminated (administratively withdrawn) from the study.

Protocol # CTN-0003 Version 7C

If a participant is hospitalized or imprisoned, he or she will be permanently discontinued from study medication and administratively withdrawn if he or she misses one full week of medication (7 consecutive days). Additionally, at any time during the study, a change in medical status that makes it unsafe for a participant to continue participating will result in study medication discontinuation and withdrawal. The Study Termination Report (STR) will reflect the appropriate reason for withdrawal/termination.

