## 7.25 Urine Drug Screen (U)

Urine drug screens are always to be collected before dispensing medications. All urine specimens will be collected using temperature controlled urine drug test cups. Urine will be collected at screening, at induction (Day –28) just prior to the first dose of Suboxone, and at each scheduled visit thereafter including each follow-up visit. For this measure, an FDA-approved one-step test will be used. Following collection of the urine sample, staff will immediately perform the test, wait for the results and record the results on the Clinic Visit CRF, following all of the manufacturer's recommended procedures.

Sites that have supplies of Jant's Accutest MultiDrug Screen-10 will use that test kit to screen urine for drugs (until the supply is exhausted). Sites that do not have, or run out of, the Accutest will use ABI's SureStep Drug Screen Card 10A. Both of these kits will test for the presence of the following 10 drugs: amphetamines, barbiturates, benzodiazepines, methadone, tricyclic antidepressants, cocaine, methamphetamine, morphine, phencyclidine, and marijuana. In addition, all sites will test for the presence of oxycodone utilizing ABM's Rapid One Oxycodone single dipstick.

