#### 9.4 Analysis Plan

Each of the primary and secondary outcome measures will be analyzed for the intent-to-treat population and for the evaluable participant population. Major differences in the results, if any, will be further explored. While there is every intention to be complete in describing the analyses to be performed, it is not possible to anticipate every contingency and some adjustments may be required to meet constraints posed by the structure of the data.

Equality of groups at baseline will be established by comparing demographic and drug use information collected on the ASI. A test of proportions will be used for main outcomes evaluated at treatment end. Continuous on-study data will be evaluated using three-factor analysis of covariance with detoxification schedule as one factor (fixed effect), stabilization dose as the second factor (fixed effect), and site as the third factor. Baseline demographic values, where they potentially affect the responses on study or where they are found to be unevenly distributed between groups at baseline despite randomization, may be investigated post hoc. Interaction effects including, but not necessarily limited to, taper schedule X dose, will be investigated post hoc. Repeated measures, survival, and time course analyses will be employed where appropriate.

Statistical tests will be two-sided at a 5% level of alpha. Confidence intervals will be two-sided with a 95% confidence coefficient.

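### The primary comparison makes no use of the Day 0 opiate urine result, so it forgoes precision from a likely strong predictor that is already collected

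*Protocol*

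**What the plan says.** **Entry to the comparison.** Protocol section 4.5: "Participants completing the pre randomization period (-28 to -1) will be randomly assigned, on day 0, to one of two taper schedules". Section 3.0 adds that in the last run-in week "participants must be on a stable dose of either 8mg, 16mg, or 24mg of buprenorphine". It stratifies randomization by that dose within site. Urine status is neither a condition nor a stratum.

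**What is collected.** Section 7.25 has urine screened at screening, at induction and "at each scheduled visit thereafter including each follow-up visit". Table 1 marks Day 0. The kit is read at once, the result goes on the Clinic Visit CRF, and urine is always taken before medication is dispensed. The taper itself begins on Day 1 (4.5).

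**What is analysed.** The primary outcome is the proportion opiate-free the day after the taper ends (9.2). Section 9.4: "A test of proportions will be used for main outcomes evaluated at treatment end". Covariance analysis with schedule, dose and site is reserved for continuous data. Baseline equality is judged on demographics and ASI drug-use information; Table 1 places the baseline ASI at screening. Baseline demographics (9.4), and factors found to differ between groups at baseline (9.7), may be explored post hoc.

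**The concern.** The outcome is a binary urine result, and the same test has been done on the same person at the point of randomization. Earlier status on a repeated measure is usually among the best predictors of later status. Here it is on the CRF for nearly everyone, since attendance is needed to be randomized. The screening ASI cannot stand in for it, because four weeks of buprenorphine separate the two.

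What is at stake is precision. Variation in outcome that Day 0 status would explain stays in the error term. Any chance imbalance in Day 0 status between arms also stays in the estimate. The protocol's own power falls to 72% with 20% dropout, so spare precision has value. If Day 0 status is brought in only after the data are seen, the analysis will look data-driven.

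**Working it through.** **Inputs from the protocol.** 240 per arm, 20% in the control group, a 12-point difference (so 32%), stated power about 82%, and 72% with 20% dropout (9.6); two-sided 5% (9.4); 1:1 allocation (4.5).

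**Assumed, not in the protocol.** The share opiate-negative at Day 0; the short-taper end-of-taper rates by Day 0 status; and a common odds ratio across the two Day 0 groups, chosen so that the long-taper arm is 32% overall.

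**Step 1: reproduce the stated power.** Pooled rate 0.26.
- Null SE = √(2 × 0.26 × 0.74 / 240) = 0.0400; alternative SE = √((0.20 × 0.80 + 0.32 × 0.68) / 240) = 0.0397.
- Power = Φ((0.12 − 1.96 × 0.0400) / 0.0397) = 85.2%.
- Reducing the difference by 1/240 as a continuity correction gives 82.7%, matching the stated 82%.
- With 192 per arm the figures are 76.6% uncorrected and 72.9% corrected, the latter matching the stated 72%.

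The comparison below is uncorrected on both sides, so its starting point is 85.2%.

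**Step 2: formula for the stratified test.** For Day 0 stratum s with m per arm, short-taper rate a, long-taper rate b and mean p:
- N = Σ (m/2)(b − a)
- V0 = Σ (m/2) p(1 − p)
- V1 = Σ (m/4)[a(1 − a) + b(1 − b)]
- Power = Φ((N − 1.96√V0) / √V1)

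With one stratum, N = 120 × 0.12 = 14.4 and V0 = 120 × 0.26 × 0.74 = 23.09, which returns 85.2%.

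**Step 3: worked example.** Suppose half are negative at Day 0, with short-taper rates of 35% (negative) and 5% (positive). The odds ratio is then 2.16 and the long-taper rates are 53.8% and 10.2%.
- N = 60 × 0.188 + 60 × 0.052 = 14.4, unchanged.
- V0 = 60 × 0.444 × 0.556 + 60 × 0.076 × 0.924 = 19.0, down from 23.1.
- V1 = 30 × (0.2275 + 0.2486) + 30 × (0.0475 + 0.0916) = 18.5.
- Power = Φ((14.4 − 1.96 × 4.36) / 4.30) = 91.3%. Simulation of 20,000 trials with a Mantel-Haenszel test gives 91.7%.

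**Step 4: range, by the same formula.**

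| Negative at Day 0 | Short-taper rate, Day 0 negative / positive | Unadjusted | Stratified |
|---|---|---|---|
| 40% | 47% / 2% | 85% | 97% |
| 50% | 38% / 2% | 85% | 94% |
| 40% | 40% / 6.7% | 85% | 92% |
| 50% | 35% / 5% | 85% | 91% |
| 20% | 50% / 12.5% | 85% | 90% |
| 50% | 30% / 10% | 85% | 88% |
| 20% | 40% / 15% | 85% | 88% |
| 50% | 25% / 15% | 85% | 86% |
| 50% | 20% / 20% (no prediction) | 85% | 85% |

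Simulations agree to within about a point.

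**Step 5: chance imbalance.** With 50% negative, the between-arm difference in Day 0 status has SD √(2 × 0.25 / 240) = 4.6 points, so about ±9 points at 95%. The plain test leaves this in the estimate.

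**Step 6: power inside a Day 0 subgroup.** With 20% negative there are 48 per arm. At 40% v 56.8% (the seventh row), power is Φ((0.168 − 1.96 × 0.102) / 0.101), about 37%. The subgroup report is therefore descriptive.

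**The case against.** **This belongs to the SAP.** Covariate choice often does, and 9.4 neither uses the word unadjusted nor excludes a stratified test of proportions. It also allows repeated-measures and time-course analyses where appropriate, and 9.5 plans baseline summaries not confined to the ASI. But the protocol does name a test for the main outcome, keeps covariance modelling for continuous data, and describes other baseline work as post hoc. A better method than the stated one is available from data already collected, so the point stands as a recommendation.

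**The gain may be small.** This stands. The larger figures need strong prediction and 40% to 50% negative at Day 0, neither documented. With weaker prediction the gain is 1 to 3 points.

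**Stronger readings a reader might infer.** None of these is supported:
- *The run-in should have required a response.* In this protocol stable means a constant dose. The stabilization-phase rule that participants "will be administratively withdrawn if they miss one full week (7 consecutive days) of medication at any time" is justified by the opportunity to stabilize on a dose. The estimand is the opiate-free proportion among all randomized. The background's remark that "some of these participants, i.e. those who achieve significant clinical improvement, may do well" is tentative and concerns tapering from maintenance.
- *Day 0 positives never stopped using.* One urine cannot show that.
- *Pooling dilutes or biases the effect.* Randomization keeps the contrast unbiased. Nor does the protocol say that Day 0 positives cannot benefit. If Day 0 negatives were 18% to 21%, the four-week rates on buprenorphine quoted in 9.6, then reaching 32% would need 14% to 17% of positives to turn negative even with no relapse: (0.32 − 0.20) / 0.80 = 15% at 20%. They would then be part of the hypothesized effect. The common odds ratio used above also lets them benefit.

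**Conclusion.** The point holds as one of efficiency. The planned primary comparison is valid, unbiased and answers a legitimate all-comers question, but it leaves out a pre-taper measurement of the outcome itself. At the protocol's own sample size and rates, stratifying by Day 0 status moves power from about 85% to between 86% and 97%, with no material loss if Day 0 status predicts nothing. The size rests on assumed Day 0 shares, assumed rates by Day 0 status and a common odds ratio; the protocol fixes none of these, so the range should be read as a range. It does not follow that eligibility is wrong or that the pooled result would mislead.

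**What to change.** In section 9.4, prespecify:
1. The primary comparison stratified by or adjusted for Day 0 opiate urine status, for example by Mantel-Haenszel, with opiate-free defined as for the end-of-taper urine. A Mantel-Haenszel risk difference keeps the result on the scale of the 12-point target.
2. Use of the randomization strata where feasible. Eleven sites, three doses and two Day 0 results make 66 cells, about 7 people each (480 / 66), so the text should say how sparse cells are pooled.
3. A rule for missing Day 0 urines that uses only pre-taper information, and a statement that the Day 0 sample is read before the randomization card is drawn.
4. The taper effect reported by Day 0 status as a descriptive secondary analysis, with its limited power noted.

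The cost is a few sentences. No new data, visits or participants are needed, and eligibility stays as it is.
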